# **ABBREVIATIONS AND DEFINITIONS OF TERMS**

Abbreviation	Definition	
E-consent	Electronic consent	
ERAS	Enhanced Recovery After Surgery	
FLACC	Face, Legs, Arms, Cry and Consolability	
PACU	Post anesthesia care unit	
PCA	Patient controlled analgesia	
PHBQ-AS	Post Hospitalization Behavior Questionnaire for Ambulatory Surgery	
POD	Postoperative day	
STAI	State-Trait Anxiety Inventory	
VR	Virtual reality	

# PROTOCOL SYNOPSIS

Study Title	Evaluation of Virtual Reality Intervention after Pediatric Idiopathic Scoliosis Surgery to Reduce Postoperative Pain and Opioid Consumption
Funder	UNC Department of Anesthesiology Research Department
Clinical Phase	N/A
Study Rationale	
 
Pain is common after surgery, and can be influenced by many factors, including anxiety
 
Distraction methods are commonly used with pediatric patients at UNC including the use of iPads postoperatively
 
Studies have shown that pain, anxiety and patient satisfaction are improved with the use of distraction
 
Studies have compared these standard distraction methods to the use of virtual reality and have shown that VR is an effective way to reduce anxiety, decrease pain, and improve patient satisfaction
 
The majority of these studies have been done either during minor procedures or preoperatively as an introduction to the patient experience
 
Little has been done to study VR in the postoperative period, particularly on the first postoperative day
 
Scoliosis surgery is a common pediatric procedure that can be associated with significant postoperative pain
 

Study Objective(s)	
 
Primary
 
To evaluate postoperative pain scores and postoperative opioid use in pediatric idiopathic scoliosis surgical patients using virtual reality as a method of immersive distraction compared with standard electronic use postoperatively.
 
Secondary
 
To evaluate patient satisfaction with use of virtual reality as a
 

Device Description	method of distraction.  The Applied VR is a lightweight mobile virtual reality headset with embedded software, creating an immersive experience. The Applied
	VR is specifically designed for medical use.
Study Design	Randomized controlled pilot study comparing virtual reality to standard electronic use (iPad) after idiopathic scoliosis surgery. Patients age 11-17 years old will be included and randomized to either the virtual reality or control (iPad) group. The randomization-and-concealment feature of REDCap data capture system will be utilized.

Subject eligibility will be verified by the research coordinator through chart review and patient questionnaire prior to enrollment in the study.

In the VR arm, VR devices will be used with pre-selected virtual reality program options. In the control arm, patients will be offered an iPad preloaded with a variety of games. Both groups of participants will also receive the postoperative standard of care including a PCA for pain control.

## Preoperatively:

- Baseline anxiety score (STAI score) will be assessed
- Baseline pain scores will be obtained: FACES scale (patient reported) and FLACC score (measured by the trained research assistant)
- Baseline vitals will be measured
- Patients will be oriented to their respective devices

#### Intraoperatively:

Must be on ERAS idiopathic scoliosis pathway at our institution

## Postoperatively:

- Must be admitted to the general pediatric floor postoperatively (versus intensive care unit)
- On POD #1 in the morning, patients in both groups will be visited by the research assistant. Patients in the VR arm will be offered the VR device for up to 30 minutes, and patients in the control arm will be offered an iPad for up to 30 minutes
- Number of hours since anesthesia end will be recorded
- Pain scores (FACES scale by the patient, FLACC scores by the research assistant) will be recorded immediately prior to intervention (T=0) and at end of intervention (T=30); FLACC score by research assistant will also be recorded at 10 minute mark (T=10)
- PCA use (in mcg or mg as appropriate) for previous hour prior to intervention (T=-60-0), during intervention (T=0-30), and one hour after intervention is complete (T=30-90) will be recorded; PCA use will be converted to morphine equivalents at time of data entry
- Total number of minutes of electronic device use will be recorded. The electronic device will be applied for a total of 30 minutes maximum, after which time the session will end
- On POD #1 in the afternoon, research assistant will return for patients in both groups, for another session up to 30 minutes. Data for both groups will be recorded as above

	If a patient declines to participate, the reason for declining will be asked for and recorded
	
 
Post-intervention:         
 
Patients and caregivers in the VR group will be given a survey regarding acceptance and effectiveness of the VR device in the postoperative period at approximately 48-72 hours
 
Patients and caregivers in both groups will be given a follow-up survey at approximately 48-72 hours and 7-10 days
 
Surveys will be conducted by phone, email or in person
 
 
 

Subject Population	Inclusion Criteria
key criteria for Inclusion	1. Subjects age 11 – 17
and Exclusion:	
 
Patients undergoing idiopathic scoliosis surgery on ERAS spine protocol (which includes postoperative PCA)
 
No contraindication to using an iPad or VR device
 

	Exclusion Criteria
	1. Patient/caregiver refusal
	2. Patients with developmental delay
	3. Patients with seizure disorder
	4. Non-English-speaking patients
	5. Patients with daily opioid use ≥ two weeks
	6. Patients with uncorrected visual or hearing impairment
	7. Patients admitted to pediatric intensive care unit on POD#1

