Both iPads and VR devices are interactive (regardless of fingers versus head movement) and this type of movement difference should not confound results. Our study aims to assess whether the VR immersive experience provides superior distraction to the standard of care (iPad use), thus by nature of the study design we are studying the difference in the two distinct types of experiences. Finger versus head movement use is inherent to the types of distraction and central to the distinct experiences. Similarly, there will be different apps between VR and iPad platforms by nature of the differences in platforms. Our goal is to examine whether an immersive experience is more beneficial than an iPad-based experience, rather than examine specific styles of games.

There will be no restriction to personal electronic use. Both groups will have access to their personal devices (cell phones, iPads) as is the standard of care. The study iPad will only be offered at specific times as designated twice a day on POD#1 for participants in the control group. Outside of the study windows, participants will not be provided with hospital iPads. Personal electronic devices including iPads are acceptable, as is the standard of care for patients to bring whatever they see fit into the hospital.

There will be a variety of popular games and apps, deemed to be content- and age-appropriate by the Child Life specialists. Program offerings will not vary by specific age or gender; our study will only include ages 11-17 and per discussion with Child Life the programs do not need to be subdivided to remain appropriate within this age range.

Standard of care for both groups will include PCA use as ordered by the surgical team as well as routine Child Life visits. The Child Life team is an integral part of pediatric postoperative recovery at UNC.

The following will be recorded: Number of hours since anesthesia end. Pain scores including FACES scale by the patient and FLACC scores by the research assistant will be recorded immediately prior to intervention (T=0) and at end of intervention (T=30); FLACC score will also be recorded at the 10 minute mark (T=10). PCA use, in mcg or mg as appropriate, for the hour prior to intervention (T=-60-0), during intervention (T=0-30), and one hour after intervention is complete (T=30-90) will be recorded. Total number of minutes of electronic device use will be recorded. PCA use will be converted to morphine equivalents at time of data entry.

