PHBQ-AS (Post Hospitalization Behavior Questionnaire for Ambulatory Surgery) – 11 items on a five-point scale (i.e., 1=Much less than before, 5=Much more than before). Total scores 11-55 (Jenkins et al, 2015)

These are all validated scoring systems in pediatric populations.

We will utilize the short STAI, as above.

Units of measurement for all variables of interest: Questionnaires and scales as above. In addition, hours since anesthesia end to start of visit (hours), PCA use (mcg or mg, at T=-60-0, 0-30, 30-90 min; converted to morphine equivalents at time of data entry), patient declines (0=Yes, 1=No), total duration of electronic device use (min), presence of dizziness (0=No, 1=Yes), presence of nausea (0=No, 1=Yes), anti-nausea medication requested during intervention (0=No, 1=Yes).

Patient and caregiver satisfaction: Qualitative satisfaction will be documented, divided into positive and negative comments.

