## **6 STATISTICAL CONSIDERATIONS**

#### 6.1 Primary Outcomes

Postoperative pain scores and postoperative PCA opioid usage surrounding intervention (in morphine equivalents).

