#### **6.3 Statistical Methods**

All statistical estimates (e.g., means, medians, proportions, incidence rates, mean differences, correlations, etc.) will be tabulated along with corresponding confidence intervals (CIs). To avoid overreliance on p-values, the magnitudes of estimates and the corresponding confidence intervals will be the primary focus of the analyses. Quantitative data analysis will occur using SAS or R and will be conducted under the supervision of a UNC Department of Anesthesiology biostatistician along with other members of the UNC Department of Anesthesiology research division.

We will work closely with our departmental statistician in all statistical analyses. After discussion with our biostatistician, we do plan to utilize a completely randomized study design. For our post-study analysis, we will perform analyses with and without gender stratification to assess whether gender is a contributing factor in opioid usage and pain scores.

For Aim 1 (comparing postoperative pain and anxiety scores), the following questionnaires and scales with validated scoring as above will be analyzed: short STAI, FACES, FLACC, PHBQ-AS.

For Aim 2 (comparing postoperative opioid usage), opioid usage will be converted into morphine equivalents at the time of data entry and analyzed.

For Aim 3 (assessing patient and caregiver satisfaction), qualitative satisfaction will be documented, divided into positive and negative comments. Patient satisfaction and overall experience are commonly linked to pain experienced during a hospitalization, and as a result, satisfaction with the use of VR as a method of pain control will be one of our outcomes.

We hypothesize that the use of virtual reality programs will provide superior distraction to standard of care and will result in improved pain scores and reduced opioid consumption after surgery. We will utilize two-sample t-test to compare the pain scores and opioid consumption in VR and control groups.

We will have the p-values reported and Bonferroni correction will be used to adjust for multiple comparison. P-values not reaching the significance level will be deemed as inconclusive.

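### The opioid primary outcome is compared without any baseline adjustment, and the only pre-session reading is one hour of PCA use; recording and adjusting for a longer pre-device baseline is an optional gain in precision

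*Combined protocol and SAP*

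**What the plan says.** The synopsis (Postoperatively) records "PCA use (in mcg or mg as appropriate) for previous hour prior to intervention (T=-60-0"), then use "during intervention (T=0-30), and one hour after intervention is complete (T=30-90"). Section 3.1 repeats the pre-session hour as "PCA use, in mcg or mg as appropriate, for the hour prior to intervention (T=-60-0"), and Section 5 lists the same three windows: "PCA use (mcg or mg, at T=-60-0, 0-30, 30-90 min; converted to morphine equivalents at time of data entry"). For the afternoon session the synopsis states "Data for both groups will be recorded as above", so a second pre-session hour is taken after the morning session. No cumulative PCA total before the first session is listed. Section 4.5 leaves intraoperative medication out of the analysis. Hours since the end of anesthesia are recorded but appear in no stated model.

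Section 6.1 names the primary outcomes as "Postoperative pain scores and postoperative PCA opioid usage surrounding intervention (in morphine equivalents"). It does not say whether the pre-session hour is a baseline, part of the outcome, or descriptive. On analysis, Section 6.3 says "We will utilize two-sample t-test to compare the pain scores and opioid consumption in VR and control groups". The only further structure there is that "we will perform analyses with and without gender stratification"; no covariate, change score or repeated-measures model is named. Allocation is completely randomised. Sections 3.3 and 6.4 set a goal of 10 completers per arm in a pilot whose effect size is unknown. Section 6.3 puts the main weight on estimates and confidence intervals.

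**The concern.** Patients differ in how much PCA opioid they use whatever device they are given. With 10 per arm, that spread largely sets the width of the interval that the plan treats as its main result and from which the next trial would be planned. Part of the spread is predictable from use before any device session. The plan collects one such reading and leaves it out of the stated test. One hour of patient-triggered doses is a small count, so even when used it may predict only weakly.

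The afternoon session adds a second difficulty. Its pre-session hour comes after the first randomised exposure. If VR has any carry-over, adjusting the afternoon outcome for that hour could remove part of the effect being estimated.

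**Working it through.** **Inputs.** From the documents: 10 per arm (3.3), two-sample t-test (6.3), windows T=-60-0, 0-30 and 30-90 (synopsis, 3.1, 5). Not given: SD, dose counts, within-patient correlation, alpha. I assume two-sided 0.05 and set the outcome SD to 1. There is no plan figure to reproduce, because N=20 comes without a power calculation (6.4).

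**Step 1: the plan as written.** CI half-width = t(0.975, 18 df) × √(2/10) = 2.101 × 0.447 = 0.94 SD. Power is 56% for a difference of 1.0 SD and reaches 80% only at 1.32 SD. Pre-session use does not enter, so a longer window on its own would change nothing.

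**Step 2: adjustment in a simple model.** Suppose each hourly reading is a stable patient level plus independent noise, and r is the correlation between two one-hour readings. A k-hour mean then has squared correlation R² = r² / (r + (1−r)/k) with a one-hour outcome, and ANCOVA leaves residual variance 1 − R². Example, r = 0.5 and k = 12: 0.25 / (0.5 + 0.5/12) = 0.46, leaving 0.54.

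| r | t-test | ANCOVA, 1 h | ANCOVA, 4 h | ANCOVA, 12 h |
|---|---|---|---|---|
| 0.3 | 1.00 | 0.91 | 0.81 | 0.75 |
| 0.5 | 1.00 | 0.75 | 0.60 | 0.54 |
| 0.7 | 1.00 | 0.51 | 0.37 | 0.32 |

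Of the variance removed by a 12-hour baseline, the existing one-hour reading already removes 9 of 25 points at r = 0.3, 25 of 46 at r = 0.5, and 49 of 68 at r = 0.7. At r = 0.5, power for 1.0 SD goes from 56% (t-test) to 68% (1 h), 78% (4 h) and 82% (12 h), ignoring chance covariate imbalance.

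**Step 3: price of the covariate.** It costs one degree of freedom and an expected imbalance factor of 1 + 1/(2×10 − 4) = 1 + 1/16. CI width relative to the t-test = (2.110/2.101) × √(1 + 1/16) × √(1 − R²) = 1.035 × √(1 − R²). Break-even correlation = √(1 − 1/1.035²) = 0.26.

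**Step 4: doses as counts.** Simulation with lognormal patient rates, lognormal hourly variation and Poisson doses, over T=0-90. Assumed: 2-4 doses per hour, between-patient CV 0.5-0.7, hourly CV 0.3-0.6.

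- One-hour covariate, independent hours: its correlation with the outcome is 0.25 to 0.67. Relative width runs from 1.035 × √(1 − 0.25²) = 1.00 (no gain) to 1.035 × √(1 − 0.67²) = 0.77 (23% narrower than the t-test).
- 12-hour pre-device rate against the planned t-test: about 0-38% narrower, never materially wider. The half-width moves from 0.94 SD to between 0.94 and 0.94 × 0.62 = 0.58 SD.

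**Step 5: 12-hour against one-hour covariate.** This turns on two unknowns: how far a patient's overnight level correlates with the session-day level, and how far adjacent hours correlate.

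- Adjacent hours independent: 9-33% narrower if the level is shared, 6-13% narrower at level correlation 0.85, and 5% narrower to 7% wider at 0.7.
- Adjacent-hour correlation 0.5, single-session outcome: 2-15% narrower if shared, 5% narrower to 4% wider at 0.85, and 1% narrower to 12% wider at 0.7.
- Adjacent-hour correlation 0.8, single-session outcome: 4% narrower to 17% wider at 0.85, and never narrower at 0.7.

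Over adjacent-hour correlations of 0.5-0.8 and level correlations of 0.7-1, the range is 16% narrower to 25% wider.

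**The case against.** The recording scheme is coherent in its own terms. It takes one hour before the session and one hour after it, which suits a short-term question about use around the intervention and does not claim to measure a patient's overall demand. The hour next to the session is also closest to it in time and state, whereas a cumulative total covers the evening of surgery and a night's sleep. Randomisation prevents bias from a short or unused baseline, and the pilot is meant to estimate an effect and test feasibility.

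Most of this stands. In particular, a reader might infer that one hour is simply too short and that the short window is why the variation remains. The documents do not support either step. They contain no reliability or correlation figure, Step 5 shows that the longer window can be better or worse, and the stated t-test ignores the reading whatever its length.

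The before-and-after argument does not rescue the analysis, because no such comparison is specified. If a simple change from the one-hour reading to a one-hour outcome were used, its variance would be 2(1 − r): 1.40, 1.00 and 0.60 at r = 0.3, 0.5 and 0.7. That is worse than or equal to no adjustment at the first two, and worse than ANCOVA (0.91, 0.75, 0.51) at all three.

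**Conclusion.** The point holds as a loss of precision. The opioid comparison carries between-patient variation that a prespecified baseline could reduce, and lack of adjustment is the main cause. The possible noise of a one-hour reading comes second and matters only once an adjusted analysis exists. Against the plan as written, ANCOVA on a pre-device cumulative rate narrows the interval by about 0-38%. That range rests wholly on assumed dose counts, CVs and correlations.

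The ranking of the two baselines is undetermined. The longer one is better if demand is stable from night to day, and can be worse if demand drifts or adjacent hours are strongly correlated. The stronger case for a value fixed before the morning session is that it precedes all device exposure and so serves both sessions, which the afternoon pre-session hour cannot do.

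That many hours of earlier PCA use exist and can be read from the pump or chart is a reasonable inference from postoperative PCA and a first session on the morning after surgery; the documents do not state it. No stated figure is wrong and no bias follows. This is an optional improvement.

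**What to change.** - At T=0 of the morning session, also record cumulative PCA use since PCA start (or over the last 12 hours), expressed as morphine equivalents per hour. Hours since the end of anesthesia are already recorded; if PCA start is used and differs from that time, note it too.
- In Section 6.3, define the opioid outcome as use after the start of the session (T=0-90) and prespecify ANCOVA for both sessions on that one baseline, fixed before the morning session. Do not use the afternoon pre-session hour as a baseline.
- Repeat the analysis with the morning T=-60-0 reading as the covariate, as a named sensitivity analysis, rather than keeping it only as a descriptive value.
- Report the correlation of each baseline with the outcome, so that the next trial can choose between them on data.

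The cost is one extra reading and REDCap field per patient, a short addition to 6.3, and one of 18 degrees of freedom. Gain will be small or absent if overnight and daytime demand are only weakly related. The field is best added before enrolment, since later retrieval may depend on what the chart retains. The model should be fixed before outcome data are compared by arm.

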## Study phases are as follows:

Screening/Consent/Baseline: Randomization and consent will be obtained preoperatively. A baseline anxiety score will be assessed on a self-report form (STAI short form). Patients in the VR arm will be oriented to the VR device before surgery. All patients will be oriented to the Wong-Baker FACES pain scale. Baseline pain scores will be obtained through the following method: FACES scale (patient reported) and FLACC score (measured by the trained research assistant). Baseline vital signs will be measured and recorded. The STAI, FACES, and FLACC scoring tools have all been used and previously validated in the pediatric population.

Intervention/Treatment: On postoperative day (POD) #1 in the morning, patients in both groups will be visited by the research assistant. Standardized scripts will be utilized by the research assistant for the entirety of the data collection. Patients in the VR arm will be offered the VR device for up to 30 minutes. Patients in the control arm will be offered an iPad for up to 30 minutes. After a total of 30 minutes maximum, the session will end. Routine data will be collected on pain scores and PCA use as below for both groups. On POD #1 in the afternoon, a research assistant will return for patients in both

groups, for another session of the respective electronic device for up to 30 minutes. If a patient declines to participate, the reason for declining will be asked for and recorded.

In the control arm of the study, the iPad will have a variety of vetted and screened games available. The content on the iPads will include puzzles, games, and movies that have been previously vetted and approved by the Child Life team, separate from this study, and are currently used as standard of care at UNC. The Child Life team is an integral part of pediatric postoperative recovery at UNC.

In the VR arm of the study, there will be selected programs to choose from. All of the content will be pleasant games or exploring programs, avoiding unpleasant and fast-moving settings such as fighting or racing. All of the content will be age appropriate, vetted and screened by the research team for violence or otherwise stressing scenarios, content requiring rapid eye motion or head movement, and content requiring more body movement than what can comfortably be done in a sitting or reclined position.

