## 4.2 Intervention/Treatment procedures (by visits)

There will be two intervention/treatment visits, both occurring on POD#1. On POD#1 in the morning, patients in both groups will be visited by the research assistant. Patients in the VR arm will be offered the VR device for up to 30 minutes. Patients in the control arm will be offered an iPad for up to 30 minutes. After a total of 30 minutes maximum, the session will end. Routine data will be collected on pain scores and PCA use as above for both groups. On POD #1 in the afternoon, a research assistant will return for patients in both groups. For participants in the intervention group, this VR session will be again offered for up to 30 minutes. Patients in the control arm will be offered an iPad for up to 30 minutes. If a patient declines to participate, the reason for declining will be asked for and recorded.

To evaluate efficacy, the following will be recorded:

- Primary outcomes:
  - Postoperative pain scores
  - Postoperative PCA opioid use surrounding intervention (morphine equivalents)
- Secondary outcomes:
  - Patient and caregiver satisfaction scores
  - Presence of dizziness/nausea
  - Time of discontinuation of VR if less than 30 minutes

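### The plan does not say how each patient's two sessions enter the two-sample t-test, and it allows post-exposure afternoon readings and overlapping PCA hours to serve as pre-session values

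*Combined protocol and SAP*

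**What the plan says.** Section 4.2 states: "There will be two intervention/treatment visits, both occurring on POD#1". Section 3.1 makes the afternoon visit "another session of the respective electronic device for up to 30 minutes", so a patient keeps one device throughout and the design is parallel, not crossover.

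The Synopsis (Study Design, Postoperatively) sets the readings for each session. FACES and FLACC scores "will be recorded immediately prior to intervention (T=0) and at end of intervention (T=30"), with an extra FLACC at 10 minutes. PCA use "for previous hour prior to intervention (T=-60-0), during intervention (T=0-30), and one hour after intervention is complete (T=30-90) will be recorded". The afternoon visit repeats this set: "for another session up to 30 minutes. Data for both groups will be recorded as above". The visits are placed only in the morning and the afternoon of POD#1, with no clock time and no minimum interval.

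Section 6.1 gives the primary outcomes as "Postoperative pain scores and postoperative PCA opioid usage surrounding intervention (in morphine equivalents"). It names no session, time point, change score or per-patient summary. The test is in section 6.3: "We will utilize two-sample t-test to compare the pain scores and opioid consumption in VR and control groups". Neither section says how two sessions from one patient are combined.

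**The concern.** Three gaps follow from the same omission.

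- **Independence.** Ten patients per arm with two sessions each give 40 session records, but only 20 independent units. A two-sample t-test on 40 records treats them all as independent.
- **Afternoon pre-session values.** Recording a new T=0 and a new preceding hour invites a within-session change. In the afternoon those values come after the morning session, so they may already reflect the assigned device.
- **PCA windows.** With no interval set, the hour after the morning session can be the hour before the afternoon one. The same doses would then count once as an outcome and once as a starting value, or twice in a total.

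The main products of this pilot are its estimates and confidence intervals (section 6.3) and an effect size for later planning (section 6.4). An interval that is too narrow, or an effect measured from a post-exposure value, would carry into the next trial.

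**Working it through.** The plan states no power, standard deviation or effect size, so there is no figure of its own to reproduce. The documents give n = 10 completed per arm, two sessions per patient, and PCA windows of T=−60 to 0, 0 to 30 and 30 to 90 minutes. The within-patient correlation r, the persistence share c and the standardised effect d are assumptions.

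**1. Pooling session records.** Let one session have variance 1 and correlation r between a patient's two sessions.
- True variance of a patient's mean: (1+r)/2. Pooling assumes 1/2, so the standard error is too small by a factor √(1+r).
- Large-sample two-sided error at a nominal 5%: 2[1 − Φ(1.96/√(1+r))].
- r = 0.3: 1.96/1.140 = 1.72, error 8.6%. r = 0.5: 1.96/1.225 = 1.60, error 11.0%. r = 0.7: 1.96/1.304 = 1.50, error 13.3%.
- Simulation of 40,000 null trials with normal data, 10 per arm and 2 sessions: 8.5%, 11.2% and 13.9%. A second run gave 8.9%, 11.6% and 14.1%.
- From the second run, coverage of a nominal 95% interval is 100 − 8.9 = 91% down to 100 − 14.1 = 86%.
- A t-test on one mean per patient holds 5.0% to 5.1%. The variance of that mean is (1+r)/2 = 0.65, 0.75 and 0.85 of a single session's.

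**2. Change from the afternoon T=0.** Let d be the between-arm benefit at the end of each session, and c the share of the morning's between-arm benefit still present at the afternoon T=0.
- Afternoon change: d − cd = d(1−c). Mean of both sessions' changes: [d + d(1−c)]/2 = d(1 − c/2).

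| c | afternoon change | mean of two changes |
|---|---|---|
| −0.25 (rebound) | 1.25d | 1.125d |
| 0 | d | d |
| 0.25 | 0.75d | 0.875d |
| 0.50 | 0.50d | 0.75d |
| 0.75 | 0.25d | 0.625d |

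- A between-arm difference in raw T=30 scores stays at d whatever c is, because nothing is subtracted.
- For scale, take d = 1.0, n = 10 per arm and two-sided alpha 0.05 (noncentral t). Power is 0.56 with no carry-over. At c = 0.5 it is 0.19 for the afternoon change alone and 0.36 for the mean of two changes. These figures ignore the different variances of change and raw scores.

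**3. Window overlap.** Let S be the minutes from morning start to afternoon start, with full 30-minute sessions. The morning after-window is [30, 90] and the afternoon before-window is [S−60, S]. For S of 90 or more, the shared time is max(0, 90 − (S−60)) = max(0, 150 − S).
- S = 90: 60 minutes. S = 105: 45. S = 120: 30. S = 135: 15. S of 150 or more: none.
- Starts at 11:30 and 13:00 satisfy the protocol. Then S = 90, and 12:00 to 13:00 is both the morning after-hour and the afternoon before-hour.

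**The case against.** A reader might infer that carry-over from the morning session hides the effect of VR. The documents do not support that, for four reasons.

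- Sections 5.1 and 6.3 compare scores and consumption between arms. They plan no subtraction of, or adjustment for, an afternoon pre-session reading, and the protocol keeps the word baseline for the preoperative measurements.
- In a parallel design a benefit that persists belongs to the effect of the assigned arm. The iPad may leave a lasting effect too, so only the between-arm difference in persistence matters.
- The direction is open. Section 5.3 allows that pain may rise once VR stops. If that lasted to the afternoon visit, an afternoon change score would overstate the VR effect.
- The morning pre-session readings precede any postoperative session and are unaffected.

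It is also fair to say that no section proposes pooling 40 records, that overlap needs a late-morning session followed by an early-afternoon one, and that overlap does harm only if the shared hour is used twice. The interval between visits can be recovered, because hours since anesthesia end are recorded at each visit.

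All of this stands, and it makes the bias conditional. It does not fill the gap: the plan neither adopts nor excludes pooling, session-specific changes or a summed PCA total. Averaging per patient is one sound choice. A morning-only primary or a repeated-measures model would also be valid if stated in advance.

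**Conclusion.** The point holds as an undefined primary analysis with three conditional consequences. Pooling the session records would raise the two-sided error from 5% to about 8.5% to 14% and cut interval coverage to about 86% to 91%, for r between 0.3 and 0.7. Using changes from the afternoon T=0 would give (1−c) of the true afternoon effect, which is too small if benefit persists and too large if pain rebounds. The same logic applies to changes from the afternoon's preceding PCA hour. Comparing raw post-session values between arms brings no such attenuation. PCA time is shared whenever full-length sessions start less than 150 minutes apart, up to a full hour at 90 minutes.

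The 150-minute limit follows from the protocol's own windows. Every value of r, c and d is an assumption, since the documents give none. The attenuation formula also assumes that both sessions end at the same between-arm difference. Nothing here shows that the trial will miss or understate a VR effect.

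**What to change.** In section 6.3:
- Name one pain time point and one PCA window as the post-session values.
- Compare one value per patient, the mean of the two sessions' post-session values.
- Adjust only for the morning T=0 pain score (pain analysis) and the morning T=−60 to 0 PCA use (opioid analysis).
- Report the afternoon T=0 and T=−60 to 0 readings as outcomes that show persistence or rebound.
- Show each session separately as description.

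In sections 3.1 and 4.2, arrange the visits so that the two sets of recording windows do not overlap, which for full sessions means starts at least 150 minutes apart. Alternatively, state that any shared PCA time is counted once. The recorded hours since anesthesia end identify overlaps if kept finely enough to show minutes.

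The cost is wording in three sections and slightly less freedom in timing the afternoon visit. No new assessments are needed, and the per-patient mean has 65% to 85% of a single session's variance at the assumed correlations.
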